With just 15 seconds of Eko DUO ECG data, a deep neural network (a form of artificial intelligence), developed at the Mayo Clinic in the US, can accurately **predict low ejection fraction, abbreviated for this study as DUO-EF**. Previous studies (n = 100) have shown DUO-EF has high accuracy for achieving this (AUC 0.906 [CI: 0.831-0.955] for EF <=35%; 0.841 [CI: 0.754 - 0.906] for EF<50%).¹⁰

Single-lead ECG requires only two contact points, as in the case of the two stainless steel electrodes on the body of the Eko DUO device, touched to the skin of the patient's chest wall for instantaneous acquisition of ECG signal. Single-lead ECG is already well established to be

adequate for a machine learning algorithm that detects atrial fibrillation, now a standard feature of some of the biggest consumer wearable technologies (e.g. Apple Watch Series 4). The Eko DUO is able to give a DUO-EF reading at the clinically significant threshold of 40% using single-lead ECG alone -- a study of 100 patients at the Mayo Clinic showed an AUC of 0.89 for detection of LVEF above or below 40%.¹¹

Eko DUO Device Regulatory Approvals

The Eko DUO device with ECG has full Conformite European (CE) marking. This study will seek approval both from the Health Research Authority research ethics committee for use of the **DUO-EF algorithm as a ‘medical device’**..

In the US, the Food and Drug Administration (FDA) has cleared Eko DUO and its AI-algorithms for heart sound interpretation and ECG detection of atrial fibrillation. The algorithm for detecting low EF recently received FDA Breakthrough Status and fast-track approval in the US. The 12-lead ECG algorithm has recently (May 2020) received Emergency Use Authorization for use during the COVID-19 pandemic.

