2. STUDY OBJECTIVES

Primary objective:

1. **To test if the DUO-EF algorithm can achieve a sensitivity and specificity above 80% for detection of LVEF above or below 40% in comparison to gold-standard echocardiography**

Secondary Objectives:

- To perform a subgroup analysis of DUO-EF against LVEF calculated by cardiac MRI (another gold standard investigation for calculating LVEF <40%)
- To validate consistency of DUO-EF result at point-of-care in GP practice ('real world' use where GP suspects new heart failure) against repeat DUO-EF at time of gold-standard investigation
- To validate consistency of DUO-EF result at point-of-care in Covid-19 follow up clinic ('real world' use where clinicians suspect new heart failure) against repeat DUO-EF at time of gold-standard investigation
- To measure if participants with DUO-EF suggestive of LVEF <40% but with gold standard investigations where LVEF >40% are at increased risk of developing heart failure at 24 months i.e. can DUO-EF predict future development of LVEF <40% at 24 months
- To evaluate DUO-EF point-of-care determination of LVEF<40% in comparison with the components of the established NICE primary care pathway (e.g. BNP result)

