3. STUDY DESIGN & METHODS

Statistical Considerations

Type of study: Prospective cross-sectional study comparing identification of LVEF above or below 40% by DUO-EF algorithm versus gold-standard methods.

Duration: Start date 01/02/2021, duration 36 months

Number and type of participants: across all settings 2,400 total

Sample Size

Imperial College Healthcare NHS Trust performs over 20,000 echocardiograms per year across its three hospital and community sites, serving the most ethnically and socioeconomically diverse population in the UK.

Based on established data and extensive clinical expertise of the investigators, around half of all patients who attend for echocardiography at the Trust are found to have LVEF <40%. **The sample size calculation below addresses the primary objective: evaluating if the DUO-EF algorithm can achieve a performance of sensitivity and specificity above 80% for detection of LVEF above or below 40% – compared to gold-standard echocardiography.**

SAMPLE SIZE CALCULATION

Primary Variable: Left Ventricular Ejection Fraction >/< 40%

Null Hypothesis: DUO-EF **DOES NOT** detect with sensitivity and specificity exceeding 80% a LVEF greater or less than 40%

Alternate Hypothesis: DUO-EF **CAN** detect with sensitivity and specificity exceeding 80% a LVEF greater or less than 40%

Type 1 error 5% (5% 2 sided test)

Type 2 error 20% (80% power)

Based on the above parameters for sample size calculation (Ref: G*Power, proportion, difference from a constant [binomial test 1 sample test]) to address the primary objective, this study will recruit participants until at least 500 have been recruited with an LVEF above 40% and 500 with a LVEF below 40% i.e the minimum total required is 1000 patients.

This will provide us with an ability to estimate sensitivity and specificity with a 95% CI $\pm 3.3\%$, and assuming the underlying sensitivity and specificity are at least 85% provide us with 80% power at the 5 % significance level to detect that they exceed the pre-specified criterion of a sensitivity and specificity of 80%.

Dropouts: Dropouts are unlikely within the context of the primary objective since consent and the entire data collection will occur within a short space of time during a single clinical visit (standard-of-care attendance for echocardiography).

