All study participants will be approached to take part and have a DUO-EF reading during the course of their routine care (minimal disruption) in the echo or cardiac MRI setting, during their GP appointment, or while attending COVID-19 follow up clinic. This will result in a large, representative study population to meet the objectives of testing the hypothesis for DUO-EF as a screening tool.

Group 1: Departmental Echocardiography and Cardiac MRI, Imperial College Healthcare NHS Trust

Unselected patients attending for departmental echocardiography (n = 1,500) and subgroup in cardiac MRI (n = 100). Patients will be consented by a member of the research team while they wait for an echocardiogram/cMRI. Patients from group 2 (GP referrals) will also be attending for an echo as part of their routine care on the heart failure pathway; they will be re-consented by a member of the research team upon arrival in the department.

Researchers will perform and record DUO-EF readings on participants and subsequently review echocardiography and cardiac MRI reports and document the LVEF calculated by these modalities.

If echocardiography does not suggest heart failure with LVEF<40% but DUO-EF does, patients will be followed-up with a **24 month phone call** (early evidence indicates the algorithm can identify low ejection fraction before being detectable on echo⁸).

Group 2: Patients in Primary care ('real world' evaluation)

NIHR North West London Primary Care **Clinical Research Network** (n = 10 GP practices). Patients attending GP with signs/symptoms of heart failure (n = 400 in total across all sites) will proceed with standard-of-care NICE heart failure pathway, with no change to standard of care through participation in study. GP's will be asked to record DUO-EF in any patient where heart failure is suspected.

Researchers will capture the point-of-care DUO-EF prediction from the GP:

- Comparing this to repeat DUO-EF ('agreement' between two time points) at time of (group 1) echocardiography (if indicated by standard of care investigations: BNP and 12-lead ECG)
- And comparing both of these DUO-EF measurements to echocardiography derived LVEF

Group 3: COVID-19 Clinic, Imperial College Healthcare NHS Trust

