Patients attending COVID-19 follow up clinic (n = 400). Only patients who are being routinely referred onto the heart failure pathway for investigations will be invited to participate i.e. patients **with clinical symptoms of heart failure**, who would/should be referred onto routine NICE pathway. Researchers will capture the point-of-care DUO-EF prediction from the Covid-19 follow up clinic setting:

- Comparing this to repeat DUO-EF ('agreement' between two time points) at time of (group 1) echocardiography
- And comparing point-of-care and time-of-echo DUO-EF results

Method for Single-Lead ECG Collection for DUO-EF

For echo and cMRI, DUO-EF recordings will be made after these gold standard investigations so as not to bias interpretation of results. The protocol for DUO-EF recording for all patients in the COVID-19 follow up clinic, GP, echo and cMRI setting will be as follows:

1. Clinical user turns on Eko DUO device and confirms connection to secure app
2. Participants sitting upright will have 15 second single-lead ECGs recorded by the Eko DUO from five different locations:
 - a. Lead I position (holding the device's electrodes between two hands)
 - b. Clavicle
 - c. Angled
 - d. V2 position
 - e. V5 position
3. Five recordings of DUO-EF recorded by researchers

The participant will be categorised as having a DUO-EF <40% if any of the five DUO-EF readings suggest this.

Data point collection: %LVEF echo, %LVEF cMRI, BNP

Recording %LVEF from echocardiography

EF is routinely measured or estimated using well-established standardized methodologies. For the purpose of this study we draw on previous work by Attia et al (2019) to record the %LVEF value on echocardiography using the first available model in a standard hierarchical sequence:

- EF determined using 3-D echocardiography¹²
- Biplane approach using the Simpson method¹³ a 2-D method, or M-mode
- In the absence of any of the preceding, the reported visually estimated EF

If the estimation is a range, the midpoint as a single LVEF value will be used. LVEF will also be classified as low ($\leq 40\%$), moderately depressed (41–49%), or normal ($\geq 50\%$).

Recording %LVEF from cardiac MRI

As with echo, standard approaches to calculating EF also exist for cMRI. Calculated %LVEF (reported as standard) will be recorded alongside classification as low ($\leq 40\%$), moderately depressed (41–49%), or normal ($\geq 50\%$).

Brain Natriuretic Peptide

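### Does calling a participant positive on any one of five readings undermine the planned 85% specificity and the stated power?

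*Protocol*

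**What the plan says.** Each participant has five 15-second recordings, one per position (section 3, Method for Single-Lead ECG Collection for DUO-EF). They are combined by a fixed rule: "The participant will be categorised as having a DUO-EF <40% if any of the five DUO-EF readings suggest this".

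The primary objective (section 2) asks whether the algorithm "can achieve a sensitivity and specificity above 80% for detection of LVEF above or below 40"%, so both measures must pass. The Sample Size Calculation in section 3 plans on "assuming the underlying sensitivity and specificity are at least 85"%, and recruitment continues until "at least 500 have been recruited with an LVEF above 40% and 500 with a LVEF below 40"%. The Protocol Allowances paragraph gives the calculated requirement as 466 per class, rounded up to 500.

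Three other statements bear on the point. Section 1.1 reports a 100-patient study that "showed an AUC of 0.89 for detection of LVEF above or below 40"%. The Performance characteristics paragraph gives the manufacturer's figures as 80% and 80%, with no combining rule named. Study Participant Population describes the purpose as "testing the hypothesis for DUO-EF as a screening tool".

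**The concern.** Under the any-of-five rule a participant is negative only when all five readings are negative. Without any model, specificity per participant cannot exceed that of the least specific position, and sensitivity cannot fall below that of the most sensitive one. Any disagreement between positions therefore moves errors onto specificity. Because both measures must exceed 80%, extra sensitivity cannot make up for lost specificity.

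The plan nevertheless uses the same 85% for both and does not say whether it applies to one reading or to the combined result. The glossary and section 1.1 describe DUO-EF in terms of one single-lead recording, so a per-reading interpretation is conceivable. In that case half of the primary conclusion could be badly underpowered. A majority rule, such as three of five, looks like an easy remedy because all five readings are recorded anyway.

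**Working it through.** **1. The plan's own figure.** Inputs from the Sample Size Calculation: null value 0.80, planning value 0.85, one-sample binomial test, "Type 1 error 5% (5% 2 sided test"), "Type 2 error 20% (80% power"). With X ~ Bin(n, p), reject when X ≥ c, where c is the smallest count with P(X ≥ c | 0.80) ≤ 0.025.

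- n = 466: c = 390, tail 0.0245, power P(X ≥ 390 | 0.85) = 80.5%.
- n = 500: c = 418, tail 0.0232, power P(X ≥ 418 | 0.85) = 82.7%.

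The smallest n reaching 80% power is 466, as stated. Each participant contributes one binary result to this calculation.

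**2. If 85% were a per-reading value, without a dependence model.** Let e be the share of participants with LVEF above 40% who are negative at a given position but positive at another. Then specificity = 0.85 − e. Power at n = 500:

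| e (points) | Specificity | Power |
|---|---|---|
| 0 | 85% | 82.7% |
| 1 | 84% | 62% |
| 2 | 83% | 39% |
| 3 | 82% | 19% |
| 5 | 80% | 2.3% |

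Eighty per cent power needs specificity of at least 84.84%, so e may be at most 0.85 − 0.8484 = 0.0016, under one participant in 500 (0.0016 × 500 = 0.8).

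**3. The same case with an assumed dependence model.** The Protocol gives no between-reading correlation, so a range is shown. With exchangeable latent normal readings of correlation ρ and z the 85% normal quantile, any-of-five specificity is the mean over a standard normal u of Φ((z − √ρ·u)/√(1−ρ))^5.

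| ρ | Specificity | Sensitivity | Power for specificity, n = 500 |
|---|---|---|---|
| 0.5 | 60% | 99% | <0.3% |
| 0.8 | 71% | 95% | <0.3% |
| 0.9 | 75% | 93% | <0.3% |
| 0.95 | 78% | 91% | <0.3% |
| 0.97 | 80% | 89% | 2.4% |
| 0.99 | 82% | 88% | 22% |
| 1 | 85% | 85% | 83% |

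Under the same premise, three-of-five keeps both measures at 85% or more and power at 83% or more throughout.

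**4. Does that premise come from the Protocol?** Step 3 holds each reading at 85% and leaves its cut-off unchanged by the rule. The Protocol states neither. Taking the AUC of 0.89 as the accuracy of one reading (equal-variance binormal), d′ = √2 × Φ⁻¹(0.89) = 1.735, and a cut-off balancing the two measures gives Φ(1.735/2) = 80.7%, not 85%. The manufacturer's figure is 80%.

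**5. The rules compared with the cut-off tuned to each.** Same AUC of 0.89 per reading, cut-off chosen so that sensitivity equals specificity under each rule, power at n = 500:

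| ρ | Any-of-five | Power | Three-of-five | Power |
|---|---|---|---|---|
| 0.5 | 84.6% | 76% | 86.0% | 95% |
| 0.8 | 82.1% | 21% | 82.6% | 29% |
| 0.9 | 81.4% | 11% | 81.6% | 13% |
| 0.95 | 81.0% | 8% | 81.1% | 9% |

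The majority rule gains 1.4 points at ρ = 0.5 and 0.1 to about 0.4 points from 0.8 upward. Equal sensitivity and specificity are therefore attainable under any-of-five once the cut-off suits the rule.

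**6. Unequal positions.** With one position at 85% and four at 75%, three-of-five gives 82%, 79%, 78% and 77% at ρ = 0.5, 0.8, 0.9 and 0.95, below the criterion from 0.8 upward. Any-of-five specificity is then 46%, 58%, 64% and 67%.

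**The case for a change.** The strongest case for a change is that the Protocol itself fixes the rule, the criterion and the planning value, so how they fit together is not a matter to leave to an analysis plan. On the participant-level reading, 85% after the rule requires each reading to have specificity of about 96.8% if readings are independent (0.85^(1/5)), 93.3% at ρ = 0.8 or 91.5% at ρ = 0.9. The Protocol offers no evidence for such values. If the manufacturer's 80% is per reading at a fixed cut-off, any-of-five specificity is at or below the null value whatever the agreement.

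Much of this stands. The direction of the effect is certain, the arithmetic is right, and 85% is not derived for the combined result. But it is not derived for a single reading either. What is left is doubt about whether the assumed 85% will be reached, and every planning value above the criterion carries that doubt. Step 5 shows that a majority vote does not remove it: with readings correlated at 0.8 or more, power is low under both rules.

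Nor is validity touched. The rule is fixed in advance and unambiguous, so sensitivity and specificity are estimated for the test as defined and the type I error is unaffected. Favouring sensitivity is a defensible choice for a screening tool.

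**Conclusion.** No change is needed. The sample size counts participants, the binomial test takes one result from each, and the recording method says how that result is formed. An analyst will apply both the 80% criterion and the 85% planning value to the any-of-five result, and on that reading the stated power holds: 80.5% at 466 and 82.7% at 500 per class. A sentence naming the unit would add clarity, but no stated figure is wrong without it.

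The large power losses arise only if 85% is a per-reading value at an unchanged cut-off, which the Protocol does not say. The choice between any-of-five and a majority vote is a fair trade-off between sensitivity and specificity. Changing it would redefine the index test for a gain of 0.1 to 1.4 points under tuned cut-offs, and with unequal positions the majority rule can itself fall below 80%. These comparisons rest on assumed correlations of 0.5 to 0.95, exchangeable latent normal readings and, for the tuned comparison, an AUC of 0.89 at every position. The five recordings are kept, so per-position and majority results can be examined without altering the plan.

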Protocol Allowances: Although we require 466 patients with EF >40% and 466 patients with EF <40% we have rounded these up to 500 patients. Furthermore, we will likely need to recruit up to 1,500 patients in total since it is unlikely that the first 1,000 patients will fulfil the exact breakdown of required LVEF above and below 40%.

Controls: The ‘control’ population in this study are participants with LVEF>40%. Indications for referral to echocardiography are broad and include but are not limited to: suspected or known

ischaemic heart disease, suspected cardiomyopathy, pericardial disease, murmurs, assessment of valve disease, assessment of prosthetic valves, assessing chronic lung disease, neurological disease (stroke or transient ischaemic attack), arrhythmia (palpitations and/or loss of consciousness), high blood pressure (common) and as a standard investigation considered before surgery. Many of these referred patients are found to have no abnormalities on echo and are otherwise healthy. Therefore, the unselected approach of this study to include all-comers to echo will generate a population sample that can be evaluated for alignment with the type of population in whom a screening programme for heart failure may be beneficial.

Performance characteristics: Eko Health (the 'manufacturer' of the algorithm) indicate a performance of 80% sensitivity and 80% specificity for the identification of LVEF above or below 40%

Confounders: our study design precludes confounders

Avoidance of bias for primary objective

To avoid any biases in both the recording of DUO-EF readings by the member of the research team and this influencing calculation of %LVEF by the echocardiography team (sonographer), the following steps will be taken:

- The member of the research team approaching patients in the echo department for consent will not be aware of the indication for referral at time-of-consent
- DUO-EF readings can happen before or after the echo, with the member of the research team unaware of the echo-derived %LVEF until they check the electronic health record (after DUO-EF has already been recorded).
- The sonographer will not be made aware of the results of DUO-EF, therefore not biasing any interpretation of %LVEF if borderline around 40%

Study Participant Population

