7. STATISTICS, DATA ANALYSIS, DATA SECURITY

Data Analysis

Data will be analysed using a statistical package and platform (R Studio). Analysis will be completed by a clinical research fellow with appropriate access privileges (including honorary Imperial NHS contract) to study data.

Data Protection, Security and Compliance

This study has been reviewed and approved by the Imperial College Healthcare NHS Trust Data Protection Office (reference 20HH6360). Data and all appropriate documentation will be stored for a minimum of 10 years after the completion of the study, including the follow-up period.

All study data will be collected using a REDCap (Research Electronic Data Capture) database, with a unique study ID for each participant (only identifiable by the principal investigator using an encrypted master key held in a password protected file on NHS servers). Patients will be allocated a de-identified study ID number, derived from a key that processes NHS numbers algorithmically. This key will be kept secure in a password encrypted file (accessible only to principal investigator). Study participant data will therefore not be identifiable unless researchers revert study ID's to NHS number.

The following data (where available) will be captured by researchers from the electronic health record (EHR):

- Encrypted NHS number (master key held in password protected file on NHS server, only accessible to principal investigator)
- Age
- Ethnicity
- Comorbidities
- Classification into study group 1-3
- BNP blood test result
- Echocardiography calculated %LVEF and categorisation
- Cardiac MRI calculated EF and categorisation

Eko DUO Data Security

The only data received by Eko Health will be digital ECG data. This will not be identifiable to the patient (i.e. not associated with an NHS number, date of birth or other identifier and Eko will not have access to the key for linkage with NHS numbers). This digital ECG data is uploaded to the Eko cloud via the mobile phone app (connected to the Eko DUO by bluetooth, no data stored on the device).

The data can be freely retrieved and will only be accessed through and securely stored within Imperial College London computers and servers. At the end of the study, all digital ECG data will be retrieved from Eko's servers and stored in accordance with Imperial College London policy on secure College computers.

No ECG or other data is stored on the mobile phone/on the app.

Interim Analysis

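### The person who documents the echo LVEF already knows the DUO-EF result, and the LVEF hierarchy does not rank biplane Simpson against M-mode, so the primary reference value could be chosen with knowledge of the index test

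*Protocol*

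**What the plan says.** Protocol section 3, *Recording %LVEF from echocardiography*, defines the primary reference value as the LVEF obtained "using the first available model in a standard hierarchical sequence". The first tier is 3-D echo, the second is "Biplane approach using the Simpson method¹³ a 2-D method, or M-mode", and the last is the reported visual estimate. For ranges the rule is fixed: "If the estimation is a range, the midpoint as a single LVEF value will be used".

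Section 3, *Study Participant Population*, Group 1, says who does the extraction and when: "Researchers will perform and record DUO-EF readings on participants and subsequently review echocardiography and cardiac MRI reports and document the LVEF".

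Section 3, *Avoidance of bias for primary objective*, lists the safeguards. The research team member does not know the referral indication at consent. The same member stays "unaware of the echo-derived %LVEF until they check the electronic health record (after DUO-EF has already been recorded"). For the echo side, "The sonographer will not be made aware of the results of DUO-EF"; the stated reason is to protect readings close to 40%.

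Section 7 lists the items captured from the health record, among them "Echocardiography calculated %LVEF and categorisation". The echo method behind the value is not on that list.

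**The concern.** The safeguards protect two steps: the DUO-EF recording from the LVEF, and the sonographer's reading from DUO-EF. A third step, taking one LVEF from the report and entering it as the reference value, is done by someone who already holds the DUO-EF result.

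That would hardly matter if every report yielded exactly one value, but the second tier does not guarantee this. If the words about a 2-D method only describe biplane Simpson, the tier holds two methods; if they name a further method, it holds three. Either way biplane Simpson and M-mode are joined by an *or*, with no stated preference.

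The value at stake is the one that classifies each participant for the primary outcome. The margin is narrow: the criterion is 80%, the design assumes 85%, and the manufacturer's quoted performance is 80% for both measures, which is the null value itself. If true performance is at that level, a shift of one or two percentage points changes the chance of a false positive conclusion. The Protocol accepts the mechanism when it blinds the sonographer because of borderline values, but it leaves the later selection step open.

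**Working it through.** **1. The plan's own figure.** Inputs from section 3, *Sample size calculation* and *Protocol Allowances*: null 80%, alternative 85%, two-sided 5%, power 80%, 466 per class rounded up to 500. An exact one-sample binomial test with upper tail 0.025 gives 466 as the first n with at least 80% power (reject at 390 or more; actual tail 0.0245; power 0.805). The normal approximation gives 471. At 500 per class the exact power is 82.7%. The stated 466 is reproduced and is not in dispute.

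**2. When a choice exists.** Upward bias needs all of the following:
- no 3-D value in the report;
- two or more second-tier values;
- those values on opposite sides of 40%;
- a selection that leans towards the DUO-EF result.

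The Protocol gives a frequency for none of these, so the size can only be shown under assumptions.

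**3. Model.** Take 500 participants per class and accuracy of 80% if the choice ignores DUO-EF (400 of 500 correct). Let f be the share of each class meeting the first three conditions, a the accuracy of DUO-EF in these participants, and w the share of choices disagreeing with DUO-EF that are switched to agree. Each switch turns a false negative into a true negative, or a false positive into a true positive. With equal classes the moves balance and each class stays at 500:

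apparent sensitivity = apparent specificity = 0.80 + f × (1 − a) × w

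**4. Numbers for f = 5%** (25 straddlers per class):
- a = 0.8, w = 0.5: 25 × 0.2 × 0.5 = 2.5 switches each way; 402.5/500 = 80.5%
- a = 0.8, w = 1: 5 switches; 405/500 = 81.0%
- a = 0.5, w = 0.5: 6.25 switches; 406.25/500 = 81.25%
- a = 0.5, w = 1: 12.5 switches; 412.5/500 = 82.5%

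**5. Effect on the test.** One measure is declared above 80% when its estimate exceeds 0.80 + 1.96 × √(0.16/500) = 0.8351. The chance of this at apparent accuracy p is Φ[(p − 0.8351)/√(p(1 − p)/500)]. At p = 0.805 it is 4.5% and at p = 0.825 it is 27.7%, against a nominal 2.5%.

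**6. Range over f** (low end a = 0.8, w = 0.5; high end a = 0.5, w = 1):

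| f | Apparent accuracy | Chance of wrongly exceeding 80%, per measure |
|---|---|---|
| 0 | 80.0% | 2.5% (nominal) |
| 2% | 80.2% to 81.0% | 3.2% to 7.7% |
| 5% | 80.5% to 82.5% | 4.5% to 27.7% |
| 10% | 81.0% to 85.0% | 7.7% to 82.5% |

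If w = 0, so that DUO-EF does not influence the choice, the upward bias is zero for every f.

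**The case against.** The strongest reply is that existing protection is substantial. Every candidate LVEF comes from a sonographer blind to DUO-EF, the researcher copies a reported number and does not read an image, and the midpoint rule settles ranges. Discretion is confined to multi-method reports near 40% without a 3-D value. This stands, and it limits the likely size. It does not close the gap, because the selection step is still unblinded.

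A second reply is that, under a rule described as hierarchical, the second tier may be meant to be read left to right, and that missing punctuation may be a drafting or text-extraction slip. That reading is plausible but not stated, and the *or* before M-mode remains under either punctuation. The fair statement is that the order is not explicit.

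Three stronger conclusions are tempting and not supported:
- *Sensitivity and specificity are biased upward.* The text shows a risk only. If methods are picked without regard to DUO-EF, the result is extra reference error, which usually lowers apparent accuracy.
- *The bias could equal the whole 5-point design difference.* The arithmetic reaches 85% only with 10% straddlers, coin-toss accuracy among them and every discordant choice switched. No figure in the Protocol supports that combination.
- *Measured and visually estimated values can never be separated later.* The method is not on the section 7 list, but a re-linkage key is held and data are kept for at least 10 years, so source reports could be consulted where they state the method.

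It is also fair that a form field for the echo method, or a supportive analysis by method, can be left to the database design or to an SAP, which is not at hand. Who extracts the LVEF, in what sequence and by which rule is different, because the Protocol already fixes it.

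**Conclusion.** The point holds as a risk to the primary reference standard. The Protocol has the LVEF documented by someone who knows the DUO-EF result, under a rule that does not always give one value, so the reference can be chosen in the light of the index test. That could raise apparent sensitivity and specificity.

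The size cannot be computed from the document. With 5% of each class straddling 40%, true accuracy of 80%, equal classes of 500, DUO-EF accuracy of 50% to 80% among straddlers, and half to all discordant choices switched, apparent accuracy would be about 80.5% to 82.5%. The upper end is a worst case for that share of straddlers, and the share itself is an assumption. The point is a cheap improvement worth making before data collection. It does not show that the primary result would be wrong.

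**What to change.** Two changes to Protocol section 3:
- Rank exactly one method per tier: 3-D, then biplane Simpson, then other 2-D, then M-mode, then visual estimate. Name the other 2-D method meant, so that each report yields a single reference value.
- Have existing staff extract and lock the LVEF without sight of that participant's DUO-EF result, before the two are linked. A team member who did not take the recording could do this by study ID. Add the step to *Avoidance of bias for primary objective*.

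Recording the echo method beside the LVEF is a useful addition but not essential.

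The cost is Protocol wording and a small reassignment of tasks, using existing reports. Accuracy may look slightly less favourable. The sample size stays at 466 per class, rounded to 500.
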